12.2.7 Safety Analysis

Safety variables will be summarised for the safety analysis set and the safety analysis set excluding post rescue treatment.

12.2.7.1 Adverse events

Individual AEs will be listed per patient and sorted by treatment group. Number of patients with adverse events (AEs), serious and leading to discontinuation of IP will be summarised by System Organ Class (SOC) and preferred term (PT) for each treatment group. AE will be considered to be treatment emergent if the onset date occurs, on or after the date of the first date of a treatment period and up to and including 1 day after the last dose is taken (or the last day of the period, if a non-IP period). A separate SOC/PT table will summarize the AEs that have been marked as hypoglycaemic symptoms.

12.2.7.2 Plasma glucose measurements

Number of plasma glucose measurements in defined ranges from glucometer assessment at home, analysed at the clinic and at the central laboratory, respectively.

12.2.7.3 Vital signs

Vital signs will be summarised at each visit and also for change from baseline for each treatment group.

12.2.7.4 ECG

ECG abnormalities will be summarised at each visit for each treatment group.

12.2.7.5 Clinical laboratory data

Descriptive statistics will be presented for the quantitative parameters overall and for all sites (since all clinical laboratory tests will be performed by a central laboratory). Changes from baseline will be summarised at each visit and shift tables produced for each treatment group.

Laboratory abnormalities will be flagged and listed, as appropriate.

12.2.8 PK/ PD Analysis

PK parameter estimates will be estimated using the NONMEM software. Parameter estimates expressing population mean, between-subject variability and random variability will be presented with their associated precision in a separate population PK/PD report. The PK/PD analysis and the report will be performed by AstraZeneca.

12.2.9 PG Analysis

The number of patients that will agree to participate in the genetic research is unknown. It is therefore not possible to establish whether sufficient data will be collected to allow a formal statistical evaluation or whether only descriptive statistics will be generated. A separate genetic report will be prepared where appropriate.

12.2.10 Extension data

Safety data obtained from the extension period will be analysed in the same way as data from the 4-month treatment period. All safety data will be presented in the clinical study report.

Any explorative work analyzing the efficacy data or PK data obtained from the extension period will be done at the discretion of the sponsor and may be included in the clinical study report or reported elsewhere.

12.3 Determination of sample size

The primary efficacy variable in this study is the change from baseline in HbA1c to final visit at 4 months. In previous studies standard deviation for change in HbA1c have varied between 1.1 and 1.4.

A sample size of 86 patients in each group will have 90% power to detect a difference of 0.7 between AZD1656 and placebo treatment arms at 4 months, assuming that the common standard deviation is 1.4 using a 2-group t-test with a 5% 2-sided significance level. Allowing for an approximate 4 to 5% drop-out rate from the primary analysis, a minimum of 90 patients will be randomized to receive study medication in each treatment group.

The number of patients that will agree to participate in the genetic research is unknown. It is therefore not possible to establish whether sufficient data will be collected to allow a formal statistical evaluation or whether only descriptive statistics will be generated. A statistical analysis plan will be prepared where appropriate.

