2. STUDY OBJECTIVES

2.1 Primary objective

- The primary objective is to compare the effect on glucose control of 4 different AZD1656 dosing regimens with placebo in type 2 diabetes mellitus patients on metformin treatment, as evaluated by the difference in HbA1c between baseline and final visit at 4 months.

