12.2.2 Multiple Treatment Comparisons

For conclusion a hierarchical closed testing procedure will be adopted for the efficacy analyses. Treatment group comparisons will be tested in dose span order whereby comparisons with placebo will commence with the highest dose regimen (randomized patient on 20mg daily titrated to maximum of 200mg daily) tested first, next dose regimen 10mg daily titrated to maximum of 140mg daily, fixed dose 40mg daily and finally the fixed dose 20mg daily. Estimates of the treatment effect and corresponding 95% confidence intervals will be presented together with the p-values for the treatment effect. All tests will be performed at the 5% level of significance.

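### The 90% power in 12.3 is correct for one stand-alone comparison with a full-size arm; under the fixed sequence in 12.2.2 the chance of a formal conclusion is about 84% for 10-140 mg and lower for the fixed doses.

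*Protocol*

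**What the plan says.** Section 12.3 bases the sample size on one comparison: "A sample size of 86 patients in each group will have 90% power to detect a difference of 0.7 between AZD1656 and placebo". The remaining inputs are given there too: "assuming that the common standard deviation is 1.4" and "using a 2-group t-test with a 5% 2-sided significance level". The SD is the top of the range reported from earlier work: "In previous studies standard deviation for change in HbA1c have varied between 1.1 and 1.4". A drop-out allowance of 4 to 5% takes 86 to 90 randomized per group.

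Section 12.2.2 sets the decision rule: "For conclusion a hierarchical closed testing procedure will be adopted for the efficacy analyses". The order against placebo is 20-200 mg, 10-140 mg, fixed 40 mg, fixed 20 mg, each at 5%. The synopsis gives the same order.

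The primary objective in 2.1 is to "compare the effect on glucose control of 4 different AZD1656 dosing regimens with placebo". Section 3.1 plans 90 patients per arm, except for 45 in each of the two fixed-dose arms.

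Section 12.3 does not mention the hierarchy and gives no power for any step after the first.

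**The concern.** The sample-size section and the decision rule concern different events. Section 12.3 gives the probability that one AZD1656-placebo test is significant. Under 12.2.2, a regimen after the first is formally concluded effective only if its own test and all earlier tests are significant. Section 12.2.2 does not spell out the stopping rule, but testing each step at the full 5% in a hierarchical order implies it.

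The power statement is worded for AZD1656 against placebo in general, and the primary objective covers four regimens. A reader will therefore tend to attach 90% to each of them, or at least to both titrated regimens. According to 3.2, the study is to support the choice of dose range for phase III. If 10-140 mg missed a formal conclusion, that would be read as a one-in-ten event on the planning assumptions, when it is closer to one in six. Part of that risk would come from a chance failure in a different arm.

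**Working it through.** **Inputs.** From 12.3: difference 0.7, SD 1.4, two-sided 5%, 86 evaluable per full-size arm. From 3.1: fixed-dose arms half the size, so 45 × 0.955 ≈ 43 evaluable (likewise 90 × 0.955 ≈ 86). From 12.2.2: the order of testing. Assumed: a true difference of 0.7 in every AZD1656 arm, since 12.3 gives one value for all.

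**The protocol's own figure.** The noncentrality is 0.7 / (1.4 × √(2/86)) = 3.28. The normal approximation gives Φ(3.28 − 1.96) = 0.906, and the exact noncentral t gives 0.903. With 85 per group the exact value is 0.8999, so 86 is the right exact answer. For drop-out, 86 / 0.955 = 90.05. Section 12.3 reproduces.

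**Stand-alone power of each test.** The two titrated arms have 0.903 each. For a fixed-dose arm (43 against 86) the noncentrality is 0.7 / (1.4 × √(1/43 + 1/86)) = 2.68, and exact power is 0.757.

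**Second step of the sequence.** Both tests use the same placebo arm, so with equal arm sizes their correlation is 0.5. The probability that both are significant is the bivariate normal probability with both limits at 3.28 − 1.96 = 1.32 and correlation 0.5, which is 0.842. Simulated two-sample t-tests give 0.839, and a simulated model with pooled variance gives 0.840. Treating the tests as independent would give 0.906² = 0.82.

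**All four steps**, by simulation of t-tests with a shared placebo arm:

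| Step | Stand-alone | In sequence (86/86/86/43/43) | In sequence (86 in every arm) |
|---|---|---|---|
| 20-200 mg | 0.903 | 0.903 | 0.903 |
| 10-140 mg | 0.903 | 0.838 | 0.837 |
| Fixed 40 mg | 0.757 | 0.673 | 0.788 |
| Fixed 20 mg | 0.758 | 0.561 | 0.748 |

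Pooling the variance over all arms changes the third column only slightly (0.905, 0.840, 0.679, 0.566). The last column separates the two causes. The sequence alone brings steps 2 to 4 to 84%, 79% and 75%; the smaller fixed-dose arms account for the rest of the fall at steps 3 and 4. If all 90 or 45 randomized patients were analysed, the sequence values would be 0.916, 0.856, 0.700 and 0.590.

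**Sensitivity of the 10-140 mg figure** (its own effect held at 0.7, 86 per arm, bivariate normal):

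- SD 1.4, 20-200 mg effect 0.5, 0.6, 0.7, 0.8, 1.0: 0.62, 0.76, 0.84, 0.88, 0.905.
- Effect 0.7 in both arms: about 0.90 at SD 1.3 and 0.975 at SD 1.1.

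**The case against.** The case for leaving 12.3 alone is that it contains no error. It names its test, level, difference and SD, and the answer is right. Sizing each comparison on its own and then controlling error with a fixed sequence is ordinary practice, and 12.3 never claims 90% for the whole sequence. All of this stands. A reader might infer that the arithmetic is wrong, or that the 90% is true of the first test only. The documents support neither: the stand-alone test of 10-140 mg against placebo also has 90.3% power. What falls to 84% is a different quantity, for which the protocol gives no figure.

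It also stands that 84% is one scenario. It takes exactly 0.7 in both titrated arms and the least favourable SD quoted. Section 12.2.6.1 adjusts for baseline HbA1c, whereas 1.4 is described as the SD of change, so the residual SD may be smaller. A reader might infer that the trial is too small. That does not follow. About 101 evaluable patients per arm would be needed for 90% on the first two steps together, but the protocol sets no such target.

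Nor are the data lost if step 1 fails. Section 12.2.2 presents estimates, 95% confidence intervals and p-values without limiting them to comparisons that pass, and 11.5.2 adds population PK/PD modelling. Only the formal conclusion is blocked.

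The argument that stepwise power can wait for the SAP is weaker. The power statement and the decision rule are both already in the protocol. The point is to say which event the printed figure describes, not to supply missing detail.

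**Conclusion.** The point holds as a matter of labelling and alignment, not of miscalculation. The 90% is per-comparison power for an arm with 86 evaluable patients. Under the written sequence, the probability of a formal conclusion equals it only for 20-200 mg. For 10-140 mg, at its full planned size, it is about 84%, a loss of some six points due to the sequence alone. For fixed 40 mg and fixed 20 mg it is about 67% and 56%. Those two should not be read as the cost of the sequence alone, because the 45-patient arms have only about 76% power even stand-alone.

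The figures assume 0.7 in every arm, SD 1.4, 86 or 43 evaluable, and no gain from baseline adjustment. The loss at step 2 is modest. It nearly disappears if the 20-200 mg effect is clearly larger than 0.7, shrinks to about one point at SD 1.1 (98.6% to about 97%), and grows quickly if the 20-200 mg effect is below 0.7.

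**What to change.** In 12.3:

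1. Describe the 90% as the power of a single comparison between a full-size AZD1656 arm and placebo.
2. Add the probability of a formal conclusion at each step of the 12.2.2 order: about 90%, 84%, 67% and 56%. State the assumptions: 0.7 in that arm and all earlier arms, SD 1.4, 86 or 43 evaluable, no gain from baseline adjustment.
3. Note that the last two figures combine the sequence with the smaller arms, and give the values with 86 evaluable throughout (about 79% and 75%).
4. Give a range for 10-140 mg, so that the scenario value is not taken as precise: about 97% at SD 1.1, and about 62% to 90% if the 20-200 mg effect is 0.5 to 1.0.

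The cost is a few sentences. No patients are added, and sample size, test order and analysis stay as they are. The only downside is that the stated power for steps 2 to 4 looks less favourable.

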12.4 Data monitoring committee (Not applicable)

13. IMPORTANT MEDICAL PROCEDURES TO BE FOLLOWED BY THE INVESTIGATOR

13.1 Medical emergency contacts

The Principal Investigator is responsible for ensuring that procedures and expertise are available to handle medical emergencies during the study. **A medical emergency usually constitutes an SAE and is to be reported as such, see Section 6.4.4**

In the case of a medical emergency the investigator may contact the Study Delivery Team Leader. If the Study Delivery Team Leader is not available, contact the Study Delivery Team Physician at ICON Clinical Research.

13.2 Overdose

In case of known or suspected overdose, symptomatic treatment as well as monitoring of vital functions, should be performed according to routine clinical practice. Plasma glucose should always be monitored and low levels of glucose treated with oral or iv glucose to counteract hypoglycaemia as prolonged episodes of hypoglycaemia may have detrimental effects on CNS, peripheral nerves and other tissues.

In order to collect more information concerning excessive doses of AZD1656 a suspected drug intake of more than 4 tablets of AZD1656/placebo at one occasion or a total daily intake of more than 6 tablets of AZD1656/placebo needs to be reported to AZ as an overdose, regardless of clinical consequences.

- An overdose with associated AEs is recorded as the AE diagnosis/symptoms on the relevant AE modules in the CRF and on the Overdose CRF module.
- An overdose without associated symptoms is only reported on the Overdose CRF module.

Overdoses with non-AZ products should be handled according to the label.

13.3 Pregnancy

Women of childbearing potential are not allowed to be included in this study and male patients must refrain from fathering a child, including sperm donation, during the study and 3 months following the last dose. If the investigator receives information that a pregnancy has occurred during the study (including pregnancy in the partner of a male patient) despite these restrictions, the designated ICON Clinical Research representative should be informed.

Appendix B
Additional Safety Information

FURTHER GUIDANCE ON THE DEFINITION OF A SERIOUS ADVERSE EVENT (SAE)

Life threatening

‘Life-threatening’ means that the subject was at immediate risk of death from the AE as it occurred or it is suspected that use or continued use of the product would result in the subject’s death. ‘Life-threatening’ does not mean that had an AE occurred in a more severe form it might have caused death (eg, hepatitis that resolved without hepatic failure).

Hospitalisation

Outpatient treatment in an emergency room is not in itself a serious AE, although the reasons for it may be (eg, bronchospasm, laryngeal oedema). Hospital admissions and/or surgical operations planned before or during a study are not considered AEs if the illness or disease existed before the subject was enrolled in the study, provided that it did not deteriorate in an unexpected way during the study.

Important medical event or medical intervention

Medical and scientific judgement should be exercised in deciding whether a case is serious in situations where important medical events may not be immediately life threatening or result in death, hospitalisation, disability or incapacity but may jeopardize the subject or may require medical intervention to prevent one or more outcomes listed in the definition of serious. These should usually be considered as serious.

Simply stopping the suspect drug does not mean that it is an important medical event; medical judgement must be used.

Examples of such events are:

- Angioedema not severe enough to require intubation but requiring iv hydrocortisone treatment
- Hepatotoxicity caused by paracetamol (acetaminophen) overdose requiring treatment with N-acetylcysteine
- Intensive treatment in an emergency room or at home for allergic bronchospasm
- Blood dyscrasias (eg, neutropenia or anaemia requiring blood transfusion, etc) or convulsions that do not result in hospitalisation
- Development of drug dependency or drug abuse.

A GUIDE TO INTERPRETING THE CAUSALITY QUESTION

The following factors should be considered when deciding if there is a “reasonable possibility” that an AE may have been caused by the drug.

- Time Course. Exposure to suspect drug. Has the subject actually received the suspect drug? Did the AE occur in a reasonable temporal relationship to the administration of the suspect drug?
- Consistency with known drug profile. Was the AE consistent with the previous knowledge of the suspect drug (pharmacology and toxicology) or drugs of the same pharmacological class? OR could the AE be anticipated from its pharmacological properties?
- Dechallenge experience. Did the AE resolve or improve on stopping or reducing the dose of the suspect drug?
- No alternative cause. The AE cannot be reasonably explained by another aetiology such as the underlying disease, other drugs, other host or environmental factors.
- Rechallenge experience. Did the AE reoccur if the suspected drug was reintroduced after having been stopped? AstraZeneca would not normally recommend or support a rechallenge.
- Laboratory tests. A specific laboratory investigation (if performed) has confirmed the relationship?

A “reasonable possibility” could be considered to exist for an AE where one or more of these factors exist.

In contrast, there would not be a “reasonable possibility” of causality if none of the above criteria apply or where there is evidence of exposure and a reasonable time course but any dechallenge (if performed) is negative or ambiguous or there is another more likely cause of the AE.

In difficult cases, other factors could be considered such as:

- Is this a recognised feature of overdose of the drug?
- Is there a known mechanism?

Ambiguous cases should be considered as being a “reasonable possibility” of a causal relationship unless further evidence becomes available to refute this. Causal relationship in cases where the disease under study has deteriorated due to lack of effect should be classified as no reasonable possibility.

Clinical Study Protocol Appendix C

Drug Substance	AZD1656
Study Code	D1020C00009
Edition Number	1.0

**Appendix C
International Airline Transportation Association (IATA) 6.2 Guidance
Document**

LABELLING AND SHIPMENT OF BIOHAZARD SAMPLES

International Airline Transportation Association (IATA) classifies biohazardous agents into 3 categories (http://www.iata.org/whatwedo/cargo/dangerous_goods/infectious_substance_s.htm). For transport purposes the classification of infectious substances according to risk groups was removed from the Dangerous Goods Regulations (DGR) in the 46th edition (2005). Infectious substances are now classified either as Category A, Category B or Exempt. There is no direct relationship between Risk Groups and categories A and B.

Category A Infectious Substances are infectious substances in a form that, when exposure to it occurs, is capable of causing permanent disability, life-threatening or fatal disease in otherwise healthy humans or animals. Category A pathogens are eg, Ebola, Lassa fever virus:

- are to be packed and shipped in accordance with IATA Instruction 602.

Category B Infectious Substances are infectious Substances that do not meet the criteria for inclusion in Category A. Category B pathogens are eg, Hepatitis A, B, C, D, and E viruses, Human immunodeficiency virus (HIV) types 1 and 2. They are assigned the following UN number and proper shipping name:

- UN 3373 – Biological Substance, Category B
- are to be packed in accordance with UN3373 and IATA 650

Exempt - all other materials with minimal risk of containing pathogens

- Clinical trial samples will fall into Category B or exempt under IATA regulations
- Clinical trial samples will routinely be packed and transported at ambient temperature in IATA 650 compliant packaging (http://www.iata.org/whatwedo/cargo/dangerous_goods/infectious_substances.htm)
- **Biological samples transported in dry ice require additional dangerous goods specification for the dry-ice content**
- IATA compliant courier and packaging materials should be used for packing and transportation and packing should be done by an IATA certified person, as applicable

- Samples routinely transported by road or rail are subject to local regulations which require that they are also packed and transported in a safe and appropriate way to contain any risk of infection or contamination by using approved couriers and packaging / containment materials at all times. The IATA 650 biological sample containment standards are encouraged wherever possible when road or rail transport is used.

Clinical Study Protocol Appendix D

Drug Substance	AZD1656
Study Code	D1020C00009
Edition Number	1

1. SAMPLING DEVICE

Blood samples (1.2 mL) for determination of AZD1656, it's metabolite AZ12555623 in plasma will be collected in 1.2 mL S-Monovette tubes from Sarstedt (article No 06.1664.001) containing K3-EDTA anticoagulant. In case of repeated sampling, catheters made of stainless steel or teflon (Venflon[®]) are used.

2. BLOOD SAMPLING

After applying a tourniquet, venous blood is taken with a disposable needle. If a catheter is used without using an obturator, the first mL of blood on each sampling occasion must be discarded.

1.2 mL of blood for determination of AZD1656 and it's metabolite AZ12555623 are collected in the sampling tubes and K3-EDTA and blood are mixed carefully and left in room temperature.

The blood samples will be centrifuged at approximately 4°C for 10 minutes at a Relative Centrifugal Force (RCF) of about 1500g within 30 minutes of the sample collection.

Following centrifugation, the plasma (approx 0.56 mL) will be transferred with a fresh pipette into a 1.8-mL polypropylene tube

. The plasma samples must be immediately frozen in upright position

3. SAMPLE LABELLING

Sample labels provided by the central lab/ CRO will be used, marked with study code, subject number, drug, scheduled time after drug administration, day, visit, sample type and unique sample identification. The label shall be used for the sample tube.

3.1 Sample list

Sample list, with the same information as on the tube labels and comments important for the analytical work, eg, additional and missing samples, must accompany the samples to the central lab/CRO as a delivery note. Sample lists should also be sent to the central lab/CRO.

3.2 Additional samples

In case the label is not available for a certain sample or when an additional sample is taken, additional labels are to be used.

4. STORAGE – NOT APPLICABLE

5. THE FROZEN SAMPLES MUST BE STORED AT -20°C. THE SAMPLES MUST BE TRANSPORTED ON DRY ICE.DELIVERY

Every batch of samples, accompanied with the sample lists, will be shipped via an agreed upon overnight courier to the central laboratory/ CRO. The samples must be packed (in the same order as on the packing list) to avoid breakage during transit, double-bagged to contain leaks and packed with a sufficient quantity of dry ice to ensure they remain frozen for at least 72 h. All applicable shipping regulations must be followed.

Clinical Study Protocol Appendix E

Drug Substance	AZD1656
Study Code	D1020C00009
Edition Number	1

